2.3 Dietary Fiber Supplementation

Dietary supplements are important factor that may regulate engraftment of beneficial donor bacteria. Short-chain fatty acids, such as butyrate, are important colonic metabolites provided by diet-based carbohydrates fermented by commensal bacteria in the gut microbiota¹⁹⁻²¹. Butyrate has been well characterized by in vitro studies to protect the epithelium against pathogens by upregulating mucins, the antimicrobial peptides responsible for the mucosal layer, and by increasing the expression of tight junction proteins to reduce intestinal permeability¹⁹. Butyrate is an inhibitor of nuclear factor NF- κ B, a transcription factor necessary for the expression of pro-inflammatory proteins²⁰, and an immunomodulator of macrophages, dendritic cells (DC), and T cells¹⁹. Studies in animal models demonstrate that supplemental butyrate upregulates regulatory T cells and ameliorates intestinal inflammation^{22,23}. Recent studies evaluated the use of various fiber-based diets in animal models of IBD with indigestible fibers having strongest effect on mucosal inflammation²³⁻²⁵. These curative properties substantiate the potential role of a post-transplant fiber therapy as necessary to prolong remission and de-escalate immunosuppressive treatments by promoting microbial engraftment and mucosal healing.

Efficacy of dietary fiber for management of IBD has been long investigated using fiber rich diet or fiber supplements, largely with variable effects. Several clinical trials have demonstrated the therapeutic benefit in UC patients with psyllium having significant effect for maintenance of remission and germinated barley for active UC²⁰. Importantly, none of the studies reported disease exacerbation or early relapse in patients with IBD. Therefore, controlled data demonstrating the effect of fiber as a prebiotic regulator of engraftment and FMT outcome in UC has yet to be explored.

2.4 Rationale

The current standard of care for ulcerative colitis relies heavily on medications targeting host factors for the management of symptoms, prevention of relapses, and induction of remission. Although there are numerous medications available for the management of UC, patients commonly become steroid-dependent and/or refractory to medical management. FMT is an emerging treatment modality for UC. Although the clinical efficacy of FMT for UC is variable, our preliminary results suggest that response may correlate with the engraftment of key beneficial microbiota¹⁸. Therefore, our study is aimed at determining the role of supplemental fiber as a mechanism to enhance the efficacy of FMT. Results from this study have the potential to offer pioneering data on the ability of prebiotics to shape microbial engraftment. This intervention has the potential to impact FMT in UC and microbial manipulation therapy more broadly.

Thus, the overall goal of this study is to test the role of supplemental psyllium in the clinical outcome and microbial engraftment of FMT for ulcerative colitis.

2.4.1 FMP Lower Delivery Microbiota Transplant (FMP250)

In our previous single-center, prospective, open-label pilot study, we sourced our two-donor fecal microbiota preparation (FMP) from OpenBiome and found that FMP delivery by colonoscopy not only was safe but also efficacious in improving clinical response as a therapeutic alternative for UC patients. Therefore, we propose to source OpenBiome's FMT Lower Delivery Microbiota Preparation (FMP250) as the investigational drug in this clinical trial.

2.4.2 Psyllium Husk Powder

Highly viscose, gel-forming soluble fibers have been found to lower elevated serum cholesterol concentrations, improve glycemic control, and have stool regularity benefits²⁸. We are interested in utilizing a fiber that can provide regularity benefits to aid in stool passage. Regularity benefits are attainable by soluble gel-forming fibers if they are able to resist fermentation and have a high-water retention capacity. We have chosen psyllium as our dietary supplement to pair with FMP250 because it is a non-fermented, natural fiber that is viscose, gel-forming, and soluble and is an FDA-approved over the counter product. Psyllium is composed of stackable polymer chains, which contribute to its viscosity, that crosslink to form a gel to promote water retention in the colon, which causes a softer stool by protecting it against dehydration. The fiber will help the stool remain whole and bulky throughout its passage in the large intestine. We chose psyllium over a very similar fiber called β -glucan because various RCTs demonstrated that fermentable fibers in the colon caused no effect on stool composition. Interestingly, psyllium has the capacity to provide regularity benefits by two mechanisms. It can either soften stool or increase bowel movements for constipation but more importantly for this study, it is able to harden stool and decreased bowel movements for diarrhea.

Psyllium husk powder will be purchased commercially by WCM investigators and provided to subjects in the fiber treatment assignment if they meet all inclusion criteria during their screening visit, excluding the endoscopic criteria.

2.5 Risk/Benefit Assessment

2.5.1 Known Potential Risks

2.5.1.1. FMT-related: (adapted from OpenBiome FMP250 Investigator Brochure V4.0):

The following adverse reactions have been reported in scientific literature to be commonly caused by FMT material within 24 hours post-procedure:

- Transient diarrhea, abdominal cramps/discomfort, and nausea
- Fever, bloating, belching, vomiting, borborygmi
- Constipation and flatulence
- Flares in IBD patients

These symptoms are usually self-limiting and of short duration. They may also be attributable to the delivery modality (e.g. colonoscopy or upper endoscopy) or underlying disease.

According to Openbiome and/or peer-reviewed literature, the following serious adverse events are potential risks that have been observed by FMT-based products (not specifically Openbiome) or included based on biological plausibility:

1. Infection
 - a. Bacterial infections from multi-drug resistant organisms (MDROs) (i.e. extended spectrum beta-lactamase (ESBL)-producing Enterobacteriaceae, vancomycin-resistant enterococci (VRE), carbapenem-resistant Enterobacteriaceae (CRE), and methicillin-resistant *Staphylococcus aureus* (MRSA))
 - b. Shiga Toxin-Producing *E. Coli* (STEC) Infections
 - c. Enteropathogenic *E. Coli* (EPEC) Infections
 - d. SARS-CoV-2 Infection
 - e. Diverticulitis, bacteremia, cytomegalovirus colitis, fever, diarrhea, encephalophagy and pancytopenia, Influenza B and diarrhea, norovirus gastroenteritis
 - f. Monkeypox Infection
2. Aspiration from upper GI delivery of FMT
3. GI complications (i.e. diarrhea, abdominal pain, appendicitis, peritonitis, IBD flare, and diverticulitis)
4. Allergy/Anaphylaxis
5. Autoimmune disorders
 - a. Exacerbation of pre-existing autoimmune conditions
 - b. Development of Rheumatoid arthritis, Sjogren's disease, peripheral neuropathy, idiopathic thrombocytopenic purpura
6. Non-infectious disease transmission (i.e. obesity, metabolic syndrome, cardiovascular disease, neurologic disorders, psychiatric conditions and malignancy)

2.5.1.2. Psyllium-related

The FDA {CFR - Code of Federal Regulations Title 21} recommends sufficient liquid consumption when taking dried psyllium husk to avoid any potential risk for choking. In geriatric patients, some rare side effects may include abdominal discomfort, nausea, mild abdominal cramps, griping, and faintness³⁴. Additionally, our investigators hypothesize that bloating could occur as a side effect.

2.5.2 Known Potential Benefits

2.5.2.1. FMT-related

Our previous pilot study found 35% of subjects clinically responded and 15% went into clinical remission when evaluated at the 4 weeks post-FMT¹⁸. Similar clinical trials found improvement in clinical response in subjects treated with FMT when compared to the placebo groups¹⁵⁻¹⁷. However, we cannot and do not guarantee that subjects will receive any benefits from this study. We hope the information learned from this study will benefit other patients with ulcerative colitis in the future.

2.5.2.2. Psyllium-related

Various dietary fiber interventions report that it may be beneficial for IBD patients, however, their results do not consistently demonstrate alleviation of disease activity and/or induction of clinical remission³¹. Therefore, we cannot and do not guarantee that subjects will receive any benefits from psyllium in combination with FMP250. We hope the information learned from this study will benefit other patients with ulcerative colitis in the future.

2.5.3 Assessment of Potential Risks and Benefits

Ulcerative colitis remains a major medical problem. Steroids, immunosuppressants, and biologic therapies are the mainstay of therapy for active disease. These medications are all associated with a range of side effects. Recent studies have demonstrated the potential efficacy of FMT for the treatment of mild to moderate UC. Although some risks exist including procedural risk associated with colonoscopic delivery, this emerging therapeutic strategy appears to be more effective than placebo in inducing clinical remission. This study will additionally assess the use of psyllium husk as a prebiotic supplement to enhance the efficacy of FMT. We do not anticipate additional risk associated with psyllium.

A FMT placebo arm with psyllium supplement is required to assess the potential clinical efficacy of psyllium alone and to serve as a placebo control for FMT. The placebo arm is required in order to determine the efficacy of FMT + psyllium over psyllium alone. However, at the end of the study, investigational FMT will be provided for patients in the psyllium + placebo arm.

Importantly, no SAEs have been found in any previous FMT intervention, including our pilot study, to be *definitely* attributed to the investigational drug. Therefore, we believe the potential benefit

of clinical and endoscopic response or remission from FMT concurrently with psyllium supplementation outweighs the risks.

2.6 Correlative Studies Background

Our collaborative team recently completed a pilot study at Weill Cornell Medicine aimed at assessing the safety, clinical efficacy, and microbial engraftment of single FMT delivery by colonoscopy for active UC¹⁸. We performed a single-center, prospective, open-label pilot study to evaluate the safety and efficacy of two-donor fecal microbiota preparation (FMP) delivery by colonoscopy. The primary outcome was clinical response at week 4 with secondary endpoints including clinical remission, mucosal healing at week 4 and safety profile. Overall, 34 patients were screened, and 20 patients were enrolled. Seven patients (35%) achieved a clinical response (Mayo score ≥ 3 and a bleeding subscore ≤ 1) by week 4. Three patients (15%) were in clinical remission at week 4 (Mayo score ≤ 2 and no subscore > 1), and two of these patients (10%) achieved mucosal healing (endoscopy subscore of 0). Paired analysis showed a significant improvement in Mayo score (Median decrease of 1.5, $p = 0.03$) and endoscopic subscore (Median decrease of 0.5, $p = 0.002$). The present will test the hypothesis that prebiotic supplementation with psyllium will increase that clinical response rate over FMT alone. Furthermore, the current study will assess additional impact on clinical and endoscopic remission rates as well as placebo FMT.

Further microbiome analysis revealed that signatures of donor-derived microbiota correlate with clinical response¹⁸. Taxonomic analysis revealed enrichment of *Ruminococcus*, *Odoribacter*, and *Christensenellaceae* in healthy donors and responders, but absent in patients with active disease. In contrast, patients who did not respond to treatment had failed to eradicate *Fusobacteria*, *Finegoldia* and *Collinsella*. To determine the fecal microbial composition and function at species/strain level, we performed metagenomic sequencing of a complete set of three samples (donor, recipient pre, recipient post) from three responder patients, who had met the primary endpoint of our pilot FMT trial. Relative abundances of microbial species were determined by Metaphlan2 and protein encoding genes profiling were determined by HUMAnN2 pipeline. Analysis of the previously identified transferrable genus of *Ruminococcus* revealed, that of the several species and strains present in the patient samples, abundance of only *Ruminococcus* torques was significantly enriched in responders. Collectively, this data revealed that response to single *colonoscopic* delivery correlated with engraftment of key species of transferrable bacteria in the responder patients. This study will therefore evaluate the hypothesis that psyllium prebiotic supplementation will change the species engraftment.

3. Study Design

3.1 Overall Design

Hypothesis: A high fiber diet will promote the engraftment of healthy donor microbiota and increase the efficacy of FMT in UC patients. If successful, this proposal will help us to define the role for dietary fiber supplementation in promoting microbial determinants of successful FMT and enhance the clinical efficacy of FMT for UC.

Study Phase: II

Study Design: Double-blinded, randomized, placebo-controlled clinical trial

Study Drug: FMT Lower Delivery Microbiota Preparation (FMP250)

Study Arms:

Group 1: Investigational FMT

- Subject will receive investigational FMT once at day 0 colonoscopy
- Subject will receive placebo FMT once at week 8 flexible sigmoidoscopy
- Observed for 12 weeks

Group 2: Investigational FMT + psyllium fiber

- Subject will receive investigational FMT once at day 0 colonoscopy
- Fiber supplementation of 1 teaspoon 2x/day for 8 weeks
- Subject will receive placebo FMT once at week 8 flexible sigmoidoscopy
- Observed for 12 weeks

Group 3: Placebo FMT with or without psyllium fiber

- Subject will receive placebo FMT once at day 0 colonoscopy
- Half of subjects will be randomized to receive fiber supplementation of 1 teaspoon 2x/day for 8 weeks
- Subject will receive investigational FMT once at week 8 flexible sigmoidoscopy
- Observed for 12 weeks

Site:

Weill Cornell Medical Center / New York Presbyterian Hospital (Clinical Facility)

- The Jill Roberts Inflammatory Bowel Disease Center at David H. Koch Center

Weill Cornell Medicine Belfer Research Building (Research Laboratory Facility)

- The Jill Roberts Institute for Research in Inflammatory Bowel Disease

Methods to Minimize Bias:

1. Randomization Bias
 - a. A series of randomized blocks of fixed size will be generated with a 1:1:1 allocation ratio. This will provide assurance that after a given block has completed subject enrollment, there will be the same number of subjects assigned to each of the three study arms. Additionally, the specific number of subjects within any randomization block (i.e., block size) will be blinded to all investigators to avoid any risk for unblinding treatment arms prior to the primary endpoint evaluation.
2. Unblinding Bias
 - a. Clinicians are blinded throughout the study so they will assess the clinical response at week 8 and will be unblinded only once this independent scoring is completed for all 135 enrolled subjects. This will reduce the risk of potential bias by the clinician as all treatment groups will receive treatment (blinded investigational or placebo FMP250) at week 8 by flexible sigmoidoscopy.

3.2 Scientific Rationale for Study Design

The ability to manipulate the human gut microbiome and alter mucosal and systemic immunity remains a central question in the study of IBD. We have previously completed a pilot study for FMT at Weill Cornell and have the clinical research infrastructure and clinical expertise to recruit patients, characterize their response, and complete the data analysis. Work from our lab and others has defined the role for specific bacteria in inducing immune responses in mouse models. We also have defined diagnostic signatures of microbial profiles associated with inflammatory disease phenotype in humans

including rheumatoid arthritis and IBD. Emerging clinical data provides evidence for the clinical efficacy of FMT in patients with ulcerative colitis (UC). Preliminary data from our own research suggests that engraftment and/or particular microbial species correlate with clinical outcome, however the factors that determine microbial engraftment are not well defined. Therefore, we designed a randomized, double-blind, placebo-controlled study to examine the possibility of improving the clinical outcome and microbial engraftment of FMP250 by using prebiotic fiber supplementation in active UC patients. Study subjects will be randomized into three groups: (1) *FMP250+Fiber*, (2) *FMP250-Fiber*, and (3) *PlaceboFMP250 with or without Fiber*. Given that fiber alone has not shown significant benefits previously in many UC studies²⁷, we hypothesize that subjects given *PlaceboFMP250+Fiber* will allow us to assess the placebo rate for FMT (*FMP250only* vs. *PlaceboFMP250+Fiber*). Also, considering that we will utilize single donor FMP250 samples, comparing subjects given *FMP250only* and *FMP250+Fiber* will allow us to scientifically assess primary endpoints of the impact of prebiotic supplement on engraftment and efficacy. *PlaceboFMP250-Fiber* will remove any risk of unblinding and will maintain the integrity of our double blinded study.

Additionally, previous reports have suggested that dietary effects of fiber can have critical effects on the microbiome²⁸. Moreover, these effects can, in part, be mediated by the impact on T cell repertoire and function²⁹. These pre-clinical data may have a critical impact on the efficacy of FMT in UC, but human data are limited. To address this limitation, we will perform metagenomic sequencing on donor and recipient samples from this trial to assess the potential impact on beneficial bacterial strain engraftment. Also, as we have previously done, immune cell characterization will be performed to assess the potential impact of fiber on T cell function.

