1.2.2 Secondary Objective(s)

To assess if a dietary prebiotic supplementation in addition to FMT compared to either alone is superior in achieving clinical remission, endoscopic response or endoscopic remission, histologic response or remission rates.

To assess clinical response / remission and endoscopic response and remission of Fecal Microbiota Transplantation (FMT) for the management of active mild to moderate Ulcerative Colitis compared to placebo.

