12.1 Sample Size and Analysis Plan

Prior studies and clinical experience involving FMT suggests a 27% response rate from a null rate of diet alone at 7%. Based on previous work¹⁸, we estimate the effect size of clinical response to FMT+fiber in patients with IBD to be approximately double the FMT-alone group (i.e., 55% vs. 27%, respectively). Recruitment of ~135 subjects with 45 patients per arm was calculated assuming a 55% response rate at 8 weeks in the FMT+fiber arm and a 27% response rate at 8 weeks in the FMT-alone arm, with approximately 80% power to detect this difference (using a two-sided significance level of 0.05)³¹. We will conduct pairwise chi-square analysis between the study arms of interests to directly address the primary study objective to detect a difference in clinical response (i.e. FMT+ fiber versus FMT alone). The remaining two pairwise comparisons can be considered as secondary aims and thus no multiple comparison adjustment is needed.

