Similar analyses will be conducted for secondary and exploratory endpoints (i.e., need for escalation, clinical remission, etc.). For secondary efficacy and safety analysis, comparison populations include: (i) FMT alone (no fiber) vs. placebo FMT alone (no fiber); (ii) FMT (with or without fiber) vs. placebo FMT (with or without fiber); (iii) placebo FMT with fiber vs. placebo FMT alone (no fiber); (iv) FMT with fiber vs. placebo FMT with fiber. All p-values will be two-sided with statistical significance evaluated at the 0.05 alpha level. Ninety-five percent confidence intervals for all parameters of interest will be calculated to assess the precision of the obtained estimates. Secondary analysis excluding subjects who discontinued the study treatment for reasons clearly not related to the study medications will also be performed. Treatment groups will be assessed at baseline with primary objective criteria. Balance between treatment groups will be assessed by ANOVA tests or Kruskal-Wallis tests for continuous variables and chi-square tests or Fisher’s exact tests for categorical variables.

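### The documents give conflicting comparators for the secondary FMT-versus-placebo objective, and some of them change psyllium as well as FMT

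*Combined protocol and SAP*

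**What the plan says.** Section 1.2.2 sets as a secondary objective the clinical and endoscopic effect of FMT "for the management of active mild to moderate Ulcerative Colitis compared to placebo". Several places then bear on how it is answered.

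- **Section 2.5.3** says the placebo arm with psyllium is needed "to assess the potential clinical efficacy of psyllium alone and to serve as a placebo control for FMT".
- **Section 3.2** says that placebo plus fibre "will allow us to assess the placebo rate for FMT (*FMP250only* vs. *PlaceboFMP250+Fiber". Its premise is: "Given that fiber alone has not shown significant benefits previously in many UC studies". Placebo without fibre is given only a blinding role: "PlaceboFMP250-Fiber* will remove any risk of unblinding and will maintain the integrity of our double blinded study".
- **Section 3.1** says of Group 3: "Half of subjects will be randomized to receive fiber supplementation of 1 teaspoon 2x/day for 8 weeks". With 45 patients in the group, that is 22 or 23 on fibre.
- **Section 12.1, first paragraph**, makes FMT+fibre versus FMT alone the primary comparison and adds: "The remaining two pairwise comparisons can be considered as secondary aims and thus no multiple comparison adjustment is needed". The two are not named.
- **Section 12.1, third paragraph**, lists four secondary comparisons. The first is "i) FMT alone (no fiber) vs. placebo FMT alone (no fiber"). The others are (ii) all FMT versus all placebo, (iii) placebo with fibre versus placebo without, and (iv) FMT with fibre versus placebo with fibre.

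Nothing says which of these answers the FMT-versus-placebo objective.

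**The concern.** A contrast estimates the effect of FMT only if the two sides are alike in everything else that was assigned. FMT without fibre against placebo with fibre changes two factors at once. So does either FMT arm against the whole of Group 3, where the fibre share is 0% or 100% on one side and about 50% on the other.

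Section 3.2 relies on fibre alone having no effect. The protocol does not support that firmly. Section 2.3 reports trials with therapeutic benefit of fibre in UC, including a significant psyllium effect on maintenance of remission. Section 2.4.2 says psyllium can reduce bowel movements in diarrhoea, and stool frequency is one of the four Mayo components (Section 10.1.1.1). Comparison (iii) in Section 12.1 examines this very premise, so it should not be assumed when the FMT control is chosen.

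At stake is the size of the reported FMT effect. A psyllium benefit would make FMT alone look weaker than it is, or would be credited to FMT in the combination arm. If the contrast were chosen after unblinding, the choice would be post hoc.

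**Working it through.** **Plan's own figure.** Section 12.1 gives 45 per arm, about 80% power, 55% versus 27%, two-sided 0.05, for the primary comparison. The unpooled normal formula gives n = (1.960 + 0.842)² × (0.55×0.45 + 0.27×0.73) / 0.28² = 44.5, so 45 per arm. Exact power of the uncorrected chi-square test at 45 versus 45 is 77.6%. The figure reproduces. No power is stated for FMT versus placebo.

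**Inputs.** FMT alone 27% and FMT+fibre 55% (Section 12.1). Placebo without fibre 7%: this is an assumption, because Section 12.1 labels 7% the null rate for diet alone. Psyllium adds d points under placebo; the documents give no value, so d runs from 0 to 15. Group 3 has 22 patients without fibre and 23 with.

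**What each contrast estimates.** Let p be the response rate on placebo without fibre, F on FMT alone and C on FMT+fibre.

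- (i): F − p
- (iv): C − (p + d)
- Section 3.2: F − (p + d) = (i) − d
- FMT alone vs Group 3: F − (p + d/2) = (i) − d/2
- FMT+fibre vs Group 3: C − (p + d/2) = (iv) + d/2
- (ii): (F + C)/2 − (p + d/2), the mean of (i) and (iv)

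In (ii) the fibre share is 45/90 = 50% on the FMT side and 22/45 to 23/45, or 49% to 51%, on the placebo side.

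| Difference in points | d=0 | d=5 | d=10 | d=15 |
|---|---|---|---|---|
| (i), fibre-matched | 20 | 20 | 20 | 20 |
| Section 3.2 contrast | 20 | 15 | 10 | 5 |
| FMT alone vs Group 3 | 20 | 17.5 | 15 | 12.5 |
| (iv), fibre-matched | 48 | 43 | 38 | 33 |
| FMT+fibre vs Group 3 | 48 | 45.5 | 43 | 40.5 |
| (ii), pooled | 34 | 31.5 | 29 | 26.5 |

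**Power.** Exact chi-square power of the Section 3.2 contrast (45 vs 23) is 51%, 27%, 13% and 6% for d = 0, 5, 10 and 15. Contrast (i), at 45 vs 22, has 52% whatever d is.

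**False positives.** Suppose FMT does nothing and d = 15. FMT+fibre responds at 7 + 15 = 22%, and Group 3 at (22×7 + 23×22)/45 = 14.7%. The chi-square test is then significant about 15% of the time, against a nominal 5%.

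**Contrast (ii), simulated.** Power for d = 0, 5, 10 and 15:

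- Mantel-Haenszel, stratified by fibre: 99.8%, 99.0%, 97.0%, 92.9%
- Unstratified, as now planned: 99.7%, 98.7%, 96.3%, 91.3%

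The largest gain is 92.9 − 91.3 = 1.6 points. With no FMT effect the stratified test rejects 4% to 5% of the time.

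**If 7% is instead the placebo+fibre rate.** Placebo without fibre is then 7 − d, so a positive d cannot exceed 7. The Section 3.2 contrast is 27 − 7 = 20 points and contrast (i) is 20 + d. The bias is still d, but the d = 10 and d = 15 columns and the 15% figure no longer apply.

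**The case against.** The best answer is that the analysis plan already handles this. The third paragraph of Section 12.1 is the only place that names secondary comparison populations. It includes (i) and (iv), which hold fibre constant, and (ii), which balances it. The Section 3.2 pairing is not on that list; it stands in a rationale and specifies no test. This stands, and it rules out the broad reading that the trial's FMT effect is confounded as planned.

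Four further points also stand.

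- Reading the two unnamed comparisons as each FMT arm against Group 3 is an inference, though the natural one with three arms. The paragraph does not call them FMT effects, and they could serve the objectives that compare the combination with either component alone.
- Placebo plus psyllium is a proper control for FMT plus psyllium. Section 2.5.3 is a problem only when that arm is also the control for FMT without fibre, as in Section 3.2.
- A reader might put the 51% power at d = 0 down to confounding. It comes from using half of Group 3; contrast (i) has only 52%.
- A reader might infer that the sections could give opposite answers. In sign that is not shown: every difference in the table is positive, and on these inputs the Section 3.2 contrast turns negative only if d exceeds 20.

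What the objection does not remove is the conflict. A confounded contrast is stated as the way to assess FMT against placebo, its premise is doubtful on the protocol's own account, and no section says that the list in Section 12.1 overrides it.

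**Conclusion.** The concern holds as a conflict between passages on a secondary objective. Sections 2.5.3 and 3.2, and probably the first paragraph of Section 12.1, point to comparators that differ in fibre as well as FMT. The third paragraph of Section 12.1 lists comparators that do not have this fault. Following the former would bias the FMT effect by d in the Section 3.2 contrast and by about d/2 against Group 3. The direction and formula follow from the design; the sizes depend on the assumed 7% and on d, which the documents do not give.

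A reader might extend this to the primary result. The documents do not support that: the primary comparison is FMT+fibre against FMT alone and does not use Group 3.

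**What to change.** Before unblinding:

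1. In Section 3.2, remove FMT only versus placebo plus fibre as the FMT-versus-placebo contrast, and align the control role given in Section 2.5.3.
2. In the first paragraph of Section 12.1, replace the two unnamed comparisons with the list in the third paragraph.
3. Name (ii), analysed by assigned fibre stratum (for example Mantel-Haenszel), as the analysis for the FMT-versus-placebo objective, and report (i) and (iv) as its stratum-specific estimates.
4. Do not describe an unstratified comparison of one FMT arm with pooled Group 3 as an FMT effect.

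The cost is wording and a stratified version of an analysis already planned; no patients or data are added. The main gain is removing the confounded contrasts, since stratifying (ii) adds at most about 1.6 points of power. There are two downsides. The stratum estimates will be imprecise, with 22 or 23 placebo patients each. A common estimate also averages effects that may differ by fibre: at d = 0 the assumed rates give odds ratios of (0.27/0.73)/(0.07/0.93) = 4.9 without fibre and (0.55/0.45)/(0.07/0.93) = 16 with it. The stratum results should therefore always be shown beside the common one.
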